Acute Treatment Phase. After randomization, and on the first day of each block of treatment, the administrator will determine the motor threshold (MT). The administrator will then deliver left prefrontal active rTMS treatment or Sham (Control) rTMS treatment for 20 to 30 sessions in blocks of 5 sessions. Patients are first tested for “remission” after the first 20 sessions of treatment and then again at the 25th and 30th sessions. “Remission” is defined as a decrease in Hamilton Rating Scale for Depression to 10 or less. **Patients will be retested for remission following the last treatment in each 5-session block.**

- If a participant remits after the first 20 sessions, the participant will enter the 24 week follow-up phase; all participants will receive a minimum of 20 treatments before being evaluated for remission;
- If a participant does not remit after the first 20 sessions of treatment, the participant will be offered an additional 5 or 10 sessions of treatment and retested for “remission” after 25 or 30 sessions. This procedure may continue for a maximum of 30 sessions total treatment.
- If the participant remits, he/she will enter the 24 week follow-up phase during which they will receive a “taper” of treatments over three weeks. The taper will include 3 treatment sessions in the first week, 2 in the second week and 1 in the last week of the taper;
- If a participant does not remit at the end of 30 sessions of treatment or drops out during treatment, the participant will be considered a treatment “failure” for the purpose of the primary analyses. The participant will enter the 24 week follow-up phase. Patients who are treatment “failures” will not receive a “taper” of treatments.

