			Screening/ Baseline	5	10	15	20	[25]	[30/ last]	1	2	3	4	8	12	16	20	24
86	Consent	S*																
01	Screening Form	S																
02	Randomization Form	B*																
03	Baseline	S																
04	Medical History	S																
05	Physical Exam	S							x									
06	Labs	S																
07	Structured Clinical Interview for DSM-IV-TR (SCID-I)	S																
08	Current/Past ATHF	S																
09	Lifetime Drinking History	B																
10	Clinician Administered PTSD Scale (CAPS)	B							x									x
11	Trauma History Questionnaire (THQ)	B																
12	Life Stressor Checklist-revised (LSC-R)	B																
13	Six-Item Blessed Orientation-Memory-Concentration (BOMC)	S																
14	Pregnancy Test	S ²	Every 4 weeks															
15	Medication Use	S	x	x	x	x	x	x	x	x	x	x	x	x	x	x	x	
16	Study Visit Form		x	x	x	x	x	x	x	x	x	x	x	x	x	x	x	
17	Audiometry: REMOVED																	
18	rTMS Treatment Log		x	x	x	x	x	x	x									
19	rTMS Taper Log									x	x	x						
20	Hamilton Rating Scale for Depression (HRSD) and MADRS	S ²	x	x	x	x	x	x	x				x	x	x	x	x	x
21	Beck Depression Inventory (BDI)	B	x	x	x	x	x	x	x				x	x	x	x	x	x
22	Quick Inventory of Depressive Symptomatology (QIDS-C16)	B	x	x	x	x	x	x	x				x	x	x	x	x	x
23	Columbia-Suicide Severity Rating Scale (C-SSRS)	S																
24	Columbia-Suicide Severity Rating Scale (C-SSRS) F/U		x	x	x	x	x	x	x	x	x	x	x	x	x	x	x	x
25	Beck Scale for Suicidal Ideation (BSS)	S	x	x	x	x	x	x	x	x	x	x	x	x	x	x	x	x
26	Beck Hopelessness Scale	S	x	x	x	x	x	x	x	x	x	x	x	x	x	x	x	x
27	Quality of Life (VR 36)	B							x									x

Assessment		Screening/ Baseline	Acute Treatment Phase						Follow-up Phase								
			4 - 11 weeks						24 weeks (6 months)								
			2-4 weeks		End of Session Number ¹				PRN Taper weeks		Weeks						
			5	10	15	20	[25]	[30/ last]	1	2	3	4	8	12	16	20	24
28	Neuropsychological Battery	B						x									x
29	DAST	S						x									x
30	PTSD Checklist (PCL)	B						x									x
31	MAST	S						x									x
32	STAXI-2	S	x	x	x	x	x	x	x	x	x	x	x	x	x	x	x
TLFB	Alcohol/Drug Timeline Followback (TLFB)		x	x	x	x	x	x	x	x	x	x	x	x	x	x	x
33	Urine Tox Screen/Alcohol Test	S		x		x		X		x		x	x	x		x	
34	Termination Form ³																x
35	Control Questionnaire	Before and after the 1 st treatment															x
36	Protocol Deviation	As required															
37	Adverse Events (AE) and ADE and Serious Adverse Events (SAEs) and UADE	As required															

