***B= Baseline**

***S= Screening**

¹ Sessions 21-25 and 26-30 may not be required if patient goes into remission earlier

² Must be conducted within 7 days prior to randomization

³ Termination Form will be completed at the end of the study OR when a patient decides to end study participation prior to the study completion date; i.e., a patient decides to withdraw or leave the study for any reason, withdraws consent, or is suspended from the study.

1. Demographics, Medical History, Physical Exam, Laboratory, Toxicology, Pregnancy

Test and Medication Use. Relevant demographics will be collected as to age, gender, racial/ethnic grouping, military history and income. In addition, a standard Medical History and Physical Exam will be completed as well as laboratory tests including a Complete Blood Count (CBC), electrolytes (chemistry), thyroid panel and a liver function test. An alcohol test and urine drug toxicology screen will be conducted prior to randomization and also randomly during the following time points of study participation:

- Acute Treatment Phase: 2nd, 4th, and 6th (if still in acute treatment) weeks
- Taper Phase: 2nd week
- Follow-up Phase: 1st, 3rd, and 5th months

A pregnancy test will be conducted on all female patients of childbearing potential (that is, all women except for those who are post menopause for > 2 years or who have a history of hysterectomy or surgical sterilization) prior to randomization and every four weeks during the study. Information on medication use (prescription, natural food products, and “over the counter”) will be collected at screening and updated after each block of five sessions during the treatment phase and every four weeks during the follow-up phase.

2. Structured Clinical Interview for DSM-IV (SCID) (First et al., 2002). The Structured Clinical Interview for DSM-IV Axis I Disorders (SCID) is a semi-structured interview that is used to make the major DSM-IV Axis I diagnoses in the most uniform manner possible.

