9. Life Stressor Checklist-Revised (LSC-R) (Wolfe & Kimerling, 1997). This is a 30-item structured clinical interview for lifetime exposure to stressful life events. The scale emphasizes a number of different potentially traumatic events and assesses the participant's emotional reaction to the stressors and the time period in which the stressors occurred. The LSC-R is reported to have sound psychometric qualities within various PTSD populations (Wolfe & Kimerling, 1997). This measure along with the Trauma History Questionnaire will be used to assess the trauma histories of our participants.

10. PTSD Checklist (PCL) (Blanchard et al., 1996). This is a 17 item self report. Its limitation is that it is keyed to a single traumatic event; e.g., the patient's worst experience in the military. Nonetheless, it has adequate reliability and has been shown to correlate well with scores from the CAPS. It will be used for follow-up of symptoms to assess change with treatment.

11. Pure Tone Audiometry. Section Removed

12. Hamilton Rating Scale for Depression (HRSD). This measure is the primary outcome measure and is completed after each block of 5 sessions throughout the study. The HRSD is the "gold standard" of randomized clinical trials for depression, and the primary measure of most rTMS studies to date. This study will utilize the 24-item version of this instrument (HRSD24) to evaluate depressed mood, vegetative and cognitive symptoms of depression, and comorbid anxiety symptoms. It provides ratings on current DSM-IV symptoms of depression, with the exceptions of hypersomnia, increased appetite, and concentration/indecision.

The Planning Committee, in making this recommendation, examined the outcome measures used in current NIH and industry trials as well as the ACNP criteria for "remission" (Rush et al., 2006). The ACNP recommends that outcome measures reflect all major criteria used in the diagnosis of MDD. Neither the HRSD or the MADRS include all criteria however, they are

widely used in clinical trials and the ACNP report notes that the field has not followed this recommendation and that if one were to use these measures for reasons of comparability (as this Planning Committee recommends), the ACNP report suggests the use of other metrics to assure that remission is complete. For that reason, the Planning Committee recommended additional use of the Quick Inventory of Depressive Symptomatology (QIDS-C16), which meets the ACNP criteria.

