Some secondary outcome measures, such as sustained response rate (“recovery”) and response on secondary outcome measures, can also be analyzed using logistic regression models. Other potential secondary analyses include continuous variables such as: change in suicidality, change in cognitive function and change in quality of life (QOL). The effect of rTMS on such continuous measures will be determined using random regression and similar techniques that maximize the use of available data in repeated measures designs.

Potential moderators of treatment response also will be analyzed using multivariate analysis of variance or regression techniques. In addition, exploratory analyses will be performed using signal detection techniques (Receiver Operator Characteristics or ROC) to attempt to identify novel moderators predictors of response. The following gives examples of some potential

analyses that may be carried out that use random regression techniques, which may be more sensitive to change than the logistic regression analyses.

a. Random regression approach to efficacy analyses

Random regression models will be used to test and evaluate treatment efficacy (see e.g., Gibbons et al., 1993). Such models trace the individual trajectories over time and, in effect, use available information to impute any missing data for comparable subjects. They thus compare the groups on a parameter describing the trajectory (e.g., the subject's response rate over time). This method not only minimizes loss of power and bias due to dropouts (for analytical purposes there are none), but also amplifies the reliability of measures using repeated measures per subject and thus usually increases power.

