Short-Term Efficacy (Baseline to End of Acute Treatment). This approach can be used to replicate and enhance the understanding of the main analyses. Data to be entered into the random regression analyses will include those collected at baseline and after sessions 10, 20 or possibly 30 if the patient receives treatment at that time. We will use a linear model on $\ln(t+1)$ to model the typical “fish hook” shape of the response trajectory, assuming an autoregressive covariance structure within individuals with treatment group as the independent variable. The primary outcome measure will be the slope of HRSD change. This random regression parallel of the primary analyses will provide complementary information to assess if rTMS is superior to sham rTMS. Secondary random regression analyses also will be performed on each of the other outcome measures. The effect of site will also be examined as in the primary analyses.

Longer-term efficacy (End of Treatment to End of Follow-up). Data to be entered into analyses will include those collected from weeks 4 to 24 of follow-up, and analytic techniques will parallel those described above. This will allow a comparison of loss of treatment effect from the end of the treatment to the end of follow-up, i.e. it will address questions of pattern of “recovery” and “recurrence.”

**b. Random regression approach to individual differences in response
(Moderators)**

Multiple regression analyses will be performed to determine if, as hypothesized, there will be individual differences in the efficacy of treatment depending upon specific predictors. This analysis will be done by adding the predictor variable and its interaction with treatment to the Random Regression Model used above. A significant interaction indicates a differential effect size depending on predictor status. Separate predictor of response analyses will be performed for each set of outcome data. These analyses are used to determine in whom or under what conditions improvement occurs. For example, we expect that younger age will predict a better response to rTMS than to sham rTMS. The initial measures to be used in these analyses will be severity of symptoms at baseline, type of comorbidity (PTSD, substance abuse, or both), duration of illness and prior treatment resistance.

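### The supportive acute-phase slope analysis lists only baseline and sessions 10, 20 and 30, so a session-25 remitter's qualifying HRSD score is not entered; the effect is small and the remedy is free

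*Protocol*

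**What the plan says.** Protocol VI.G item 12 says of the HRSD: "This measure is the primary outcome measure and is completed after each block of 5 sessions throughout the study". Table 2 in the same section marks it at screening and at the ends of sessions 5, 10, 15, 20, [25] and [30/last].

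Protocol VI.E tests for remission (HRSD of 10 or less) "after the first 20 sessions of treatment and then again at the 25th and 30th sessions". A patient who remits leaves acute treatment at that point; the first footnote to Table 2 says: "Sessions 21-25 and 26-30 may not be required if patient goes into remission earlier".

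Protocol VIII.C.a, under short-term efficacy, then sets the input to the slope model: "Data to be entered into the random regression analyses will include those collected at baseline and after sessions 10, 20 or possibly 30", the last conditional on treatment at that time. The model is linear in ln(t+1) with an autoregressive within-patient covariance, and the outcome is the HRSD slope. The paragraph runs from baseline to the end of acute treatment and presents the model as the random-regression counterpart of the primary analysis. Section VIII.C justifies such methods by their full use of the repeated measures collected.

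**The concern.** Sessions 5, 15 and 25 are rated but not listed. Session 25 matters most, because its score decides whether a patient goes on to session 30.

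A session-25 remitter was not in remission at session 20, so the session-20 HRSD was above 10. That patient has no session-30 score. The last listed score is therefore always a non-remitted one, although the primary analysis counts the patient as a success.

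Random regression handles an absent value safely when the absence depends only on scores in the model. Here the session-30 score is absent because of the session-25 score, which is outside it. Session-20 remitters do not raise this problem, since their stopping score is listed. What is at stake is a supportive estimate slightly biased towards no difference and some avoidable loss of precision.

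**Working it through.** **The plan's own figure.** The protocol gives no figure for the slope analysis. Its one design figure is 81% power for remission, 6% sham against 16% rTMS, 180 per group (VIII.A). With a continuity correction and two-sided 0.05 (two-sided is an assumption), se0 = √(2 × 0.11 × 0.89/180) = 0.0330 and se1 = √((0.06 × 0.94 + 0.16 × 0.84)/180) = 0.0326. Then z = (0.10 − 1/180 − 1.96 × 0.0330)/0.0326 ≈ 0.92, a power of 82.0%, close to 81%. Without the correction it is 86.1%. Only the 6% and 16% are used below.

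**Scores left out**, from Table 2 and VIII.C.a:

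| Last session | Post-baseline scores collected | Listed | Left out |
|---|---|---|---|
| 20 | 4 | 2 | 2 (50%) |
| 25 | 5 | 2 | 3 (60%) |
| 30 | 6 | 3 | 3 (50%) |

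**Precision.** The slope variance is the slope element of (X′V⁻¹X)⁻¹, with X = (1, ln(t+1)) and V containing autoregressive errors. The protocol gives no HRSD variances, correlations or time unit. Assumed: error SD 5, lag-one correlation 0.3 to 0.9, random-slope SD 0 to 4, and a patient with all visits. The ratio of standard errors, listed schedule to full schedule, is:

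- t in weeks: 1.004 to 1.032, so variance 1.004² = 1.008 to 1.032² = 1.065.
- t in sessions: 1.004 to 1.087, so variance 1.008 to 1.087² = 1.182.

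The loss is modest because most of the information on a slope lies at the ends of the schedule.

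**Bias.** Simulated with 400,000 patients per arm, mean baseline 27 (assumed), autoregressive errors with SD 5, mean slopes set to give about 6% and 16% remission, stopping at HRSD of 10 or less at session 20 or 25, and generalised least squares with the true covariance. Standard errors and power are scaled to 180 per arm:

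| Time unit, slope SD, correlation | True difference | All scores | Listed scores | Shrinkage | SE, all / listed | Power, all / listed |
|---|---|---|---|---|---|---|
| weeks, 2, 0.5 | −1.730 | −1.735 | −1.685 | 2.6% | 0.419 / 0.423 | 98.5% / 97.9% |
| weeks, 3, 0.5 | −2.170 | −2.166 | −2.114 | 2.6% | 0.481 / 0.485 | 99.4% / 99.2% |
| weeks, 3, 0.3 | −2.094 | −2.080 | −2.027 | 3.2% | 0.476 / 0.485 | 99.2% / 98.7% |
| sessions, 1.5, 0.5 | −1.137 | −1.143 | −1.121 | 1.4% | 0.249 / 0.253 | 99.6% / 99.3% |

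The full schedule recovers the true difference to within 1%. A separate simulation with independent residuals and random intercepts gave −2.448 on the listed scores and −2.482 on all scores against a true −2.487. Shrinkage on the listed scores is 1 − 2.448/2.487 = 1.6%, and its range over assumptions was about 1% to 2.5%.

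**Patients affected.** In the independent-residual simulation, session-25 remitters were about 31% of active and 32% of sham remitters: 180 × 0.16 × 0.31 = 8.9 and 180 × 0.06 × 0.32 = 3.5, together 12.4, or 3.4% of 360. The autoregressive runs give 12 to 13.

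**The case against.** The strongest reply is about status. VIII.C introduces these models as examples of analyses that may be carried out, and VIII.E says the list is not complete. The sentence says what data will be included, not that nothing else will be. This stands in part: the analysis is supportive, and the protocol does not forbid other scores. But the list names particular sessions and sets a condition on the last one, which would have no purpose if every block score were meant. Nor is this detail left to a later plan: the time points are stated, and a better choice from data already collected is available.

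A second reply is that the [30/last] column of Table 2 would hold a session-25 final score. VIII.C.a, however, asks for treatment at session 30, not for the last score.

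Several stronger readings are tempting and not supported:

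- A reader might infer a heavy precision loss from the omission of half the scores. A variance increase of 8% to 26% appears only with independent residuals, not under the autoregressive structure the protocol states.
- A reader might infer that every other outcome loses its end-of-acute value in session-25 remitters. Several measures, such as the CAPS and VR-36, have a single acute post-baseline rating in the [30/last] column, and for these the 30 may well mean that column, given the paragraph's baseline-to-end-of-acute scope. The loss follows only on a strict reading.
- A reader might take the remark about dropouts, "for analytical purposes there are none", as refuted. It describes a method that keeps incomplete patients in the analysis, and session-25 remitters stop by protocol; they do not drop out.

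**Conclusion.** The point holds as a minor one. On the wording of VIII.C.a, the score that ends treatment at session 25 is not entered, and the missing session-30 value is then not missing at random given the data in the model. That conflicts with the section's own reason for choosing random regression. The counts of omitted scores and the last listed score above 10 follow from the text alone.

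The sizes in the working rest on assumed variances, correlations, time unit and timing of remission. The shrinkage is towards no difference, hence conservative. The power change of under 1 point comes from scenarios already at 98% power or more, where little change could show. A reader might infer that the trial's main conclusion is at risk. It is not: the primary logistic regression on remission counts session-25 remitters as remitters.

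**What to change.** In Protocol VIII.C.a, replace the list of time points with: *baseline and every acute-phase assessment collected (for HRSD, sessions 5, 10, 15, 20, 25 and 30/last), through the last acute session*. Apply the same rule to the other outcomes, so that a measure rated once at the end of acute treatment enters at whichever session was the patient's last. The session-25 stopping score is then in the model, and the simulated shrinkage goes away. The cost is one sentence: no new data, no extra visit and no change to the primary analysis.

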To randomize a patient into the study, the SI or the SC will submit the electronic randomization form. This computerized system, after verifying eligibility, will randomize a patient to either the rTMS or to the sham rTMS treatment group. A non-sequential treatment number will be assigned. This unique treatment number will be key entered into the device which will be associated with a treatment assignment and will enable the rTMS device to deliver the appropriate treatment (active or sham) to each patient. Every attempt will be made to randomize a participant so that he/she will receive his/her first rTMS treatment as soon as possible after randomization. Non-sequential treatment numbers will be assigned to ensure that investigators cannot initiate a participant on treatment before randomization. An adaptive randomization scheme will be used so that approximately equal numbers of patients will be randomized to each treatment group within several important subsets. These subsets include patients with a substance abuse disorder and patients with PTSD. Enrolling site will also be

incorporated into the adaptive randomization scheme. A “biased coin” procedure will be used to make an assignment that will improve overall balance more likely than an assignment that will not (Efron 1971). Imbalance will be calculated by summing the marginal totals for these three factors for each treatment group and calculating the difference, D. If the imbalance is less than three, assignments will be made with equal probability; otherwise, the probability of assigning to the group that will increase imbalance will be $1/D$. This approach will be incorporated within the electronic data capture system.

D. Duration of the Study

The duration of the study will be three and a half years, with a three year enrollment period. Each participant will be in the trial for a total of approximately 29-39 weeks (2-4 weeks screening, 4-11 weeks acute treatment phase and 24 week follow-up phase).

E. Intervention Procedure

The overview of the experimental design and procedures is presented in Figure 2.

[figure not shown]

Figure 2: Overview of Research Design

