Site effects will be tested using a logistic regression analysis examining the effect for Treatment in a model that includes Site and Site x Treatment interaction. Baseline comparability among the treatment groups will be evaluated with respect to such variables as demographics (e.g., age, gender, race), baseline values of outcome measures (e.g., the HRSD, QOL measure(s), suicidality, etc.), antidepressant currently being used, etc. Chi-square and analysis of variance techniques, as appropriate, will be used to determine any differences in distribution of the variables across the treatment groups. Any variable that appears to be different between the groups ($p < 0.10$) will be evaluated to determine whether such imbalances had any effect on conclusions.

2. Analysis of Primary Outcome Measure

The primary outcome measure in this study is success or failure to achieve remission from depression after a maximum of 30 sessions of rTMS or sham treatment. “Remission” is defined by a score on the HRSD24 of 10 or less after a maximum of 30 sessions of treatment. The primary analysis will be done as an “intent-to-treat” analysis, i.e. patients will be analyzed in the groups to which they were randomized, and patients who dropout before completing the Acute Treatment Phase will be considered treatment failures for the primary analysis on remission rates. The primary analyses and several secondary analyses will be conducted on outcome measures such as “remission” and “response” which are binary and defined by specific criteria. Logistic regression models with PTSD diagnosis, history of substance abuse, and site as covariates will be used for these analyses.

C. Additional Analyses

In addition to the main analysis using the entire randomized or “intent-to-treat” cohort, logistic regression models will be used for “completers” and also for “fully compliant” subjects to provide further information about treatment effects. For example, it would be expected that if rTMS had a significant clinical effect, its effect would appear greater in “completer” and “totally compliant” cohorts, than in the entire randomized cohort. Other analyses will be performed on secondary measures to further provide useful clinical information.

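### The random-regression efficacy model leaves out PTSD and substance abuse, which balance the randomisation and are in the primary model; its test is somewhat conservative if they predict the HRSD course (minor)

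*Protocol*

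**What the plan says.** - **Randomisation (Protocol VI.C).** A biased-coin scheme balances the arms within subsets: "These subsets include patients with a substance abuse disorder and patients with PTSD". Enrolling site is the third factor. When the imbalance D is below three, both arms are equally likely; "otherwise, the probability of assigning to the group that will increase imbalance will be" 1/D.
- **Primary analysis (VIII.A and VIII.B.2).** "Logistic regression models with PTSD diagnosis, history of substance abuse, and site as covariates will be used for these analyses".
- **Random-regression model (VIII.C.a, short-term efficacy).** The model is linear in ln(t+1), "assuming an autoregressive covariance structure within individuals with treatment group as the independent variable". The parameter is fixed too: "The primary outcome measure will be the slope of HRSD change". On covariates the paragraph adds one sentence: "The effect of site will also be examined as in the primary analyses". On its role it says: "This random regression parallel of the primary analyses will provide complementary information to assess if rTMS is superior to sham rTMS". The longer-term analysis is to use the same techniques, and the model is extended to the other outcome measures.
- **Moderators (VIII.C.b).** Type of comorbidity enters here, as a predictor added to the random-regression model together with its treatment interaction. The base model therefore does not contain it.
- **Status (VIII.C).** The section is introduced as giving examples of potential "analyses that may be carried out that use random regression techniques".

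**The concern.** Balancing the allocation on a prognostic factor removes that factor's contribution to chance differences between arms, so the true sampling variance of the treatment contrast falls. A model without the factor leaves its variance in the residual. The reported standard error then describes a less well balanced trial than the one that was run. It is too large, and the test rejects less often than its nominal level.

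The protocol treats PTSD and substance abuse as important enough to balance on and to adjust for in the primary model. It then writes out a model meant to parallel that primary analysis and leaves both out. VIII.C presents random regression as potentially more sensitive than the logistic analyses and as usually gaining power. Omitting known balancing factors works against that purpose. At stake is some precision in a supportive analysis of HRSD slope and in other outcomes analysed the same way.

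**Working it through.** **Inputs from the protocol.** 360 patients, 180 per arm (VIII.A). Nine sites, about 40 patients each (VI.A). Balancing on PTSD, substance abuse and site with the 1/D rule (VI.C). PTSD 39% and substance abuse 45% among veterans with a depressive disorder (I.I.2).

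**Inputs assumed.** R², the share of slope variance explained by PTSD and substance abuse together, is not given; the range used is 0% to 20%. Alpha is taken as 0.05 two-sided. VIII.A states none; X.B.3 uses 0.05 in its monitoring example.

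**The plan's own figure.** VIII.A states 81% power for 6% versus 16% remission with 180 per arm. A two-proportion test gives 86.1% (pooled normal), 83.3% (Fisher exact) and 82.0% (continuity-corrected). The stated 81% is therefore close to the continuity-corrected value. It belongs to the binary primary outcome. No power is stated for the slope model, so 81% serves below only as a convenient anchor for the adjusted model.

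**Formulas, assuming near-perfect balance.**
- Ratio of unadjusted to correct standard error: k = 1/√(1 − R²).
- True type I error of the unadjusted test: 2Φ(−1.96k).
- Power of the unadjusted test: Φ(2.838 − 1.96k), where 2.838 = 1.96 + 0.878 corresponds to 81% power when adjusted.

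Example at R² = 10%: k = 1/√0.90 = 1.054 and 1.96k = 2.066. Type I error is 2Φ(−2.066) = 3.9%. Power is Φ(2.838 − 2.066) = Φ(0.772) = 78.0%.

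**Simulation.** The biased coin was run with the inputs above, 3,000 trials per setting. Per-patient slopes on ln(t+1) were compared between arms with and without the two factors, each factor carrying half of R².

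| R² (assumed) | SE inflation, formula | Type I error without factors: formula / simulated | Power without factors, formula (81% with) | Simulated power, without vs with |
|---|---|---|---|---|
| 0% | 0% | 5.0% / 5.0% | 81.0% | 81.2% vs 81.1% |
| 5% | 2.6% | 4.4% / 4.6% | 79.6% | 79.1% vs 80.5% |
| 10% | 5.4% | 3.9% / 3.8% | 78.0% | 76.8% vs 79.9% |
| 20% | 11.8% | 2.8% / 2.4% | 74.1% | 74.0% vs 81.1% |

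With both factors in the model, simulated type I error was 4.9% to 5.4%. At R² = 20% the unadjusted model reported a mean standard error of 0.088 against a true spread of 0.078 to 0.079.

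**What a given R² requires.** With independent factors of equal effect b (in slope SDs), R² = b²(0.39 × 0.61 + 0.45 × 0.55) = 0.485b². So 5% needs b ≈ 0.32, 10% needs b ≈ 0.45 and 20% needs b ≈ 0.64 for each factor.

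**Main effects or time interactions.** A 400-run check used a repeated-measures model with autoregressive errors and allocation balanced within PTSD-by-substance-abuse cells. When the factors acted on slope only, the mean standard error was 0.0695 without them, 0.0686 with main effects and 0.0677 with factor-by-time terms. Main effects alone recovered half of the correction.

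**The case against.** The strongest reply is that VIII.C.a does not say treatment is the only independent variable. VIII.C offers these models as examples, VIII.E calls the list a brief outline, and covariates of a supportive mixed model are usual material for a statistical analysis plan, which was not available here. This lowers the weight of the point but does not remove it. The paragraph fixes the time scale, covariance structure, data points, tested parameter and independent variable, and then names one further factor, site. VIII.C.b adds comorbidity to that model as something new. The model is stated, and on covariates it departs from the analysis it is meant to parallel.

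Four stronger readings are tempting, and the documents do not support them.
- A reader might infer that all three balancing factors are ignored. Site is to be examined as in the primary analyses, where it is a covariate and its interaction with treatment is tested (VIII.B). The firm gap is PTSD and substance abuse.
- A reader might infer that a material power loss is established. No document gives the factors' strength. At R² up to 5% the loss is under 1.5 points, and 10% already needs each factor to shift slope by about 0.45 SD.
- A reader might infer that quality of life and cognition suffer equally. Table 2 collects them only at baseline, the end of acute treatment and week 24, so the model built on sessions 10, 20 and 30 does not directly describe them. VIII.C also allows similar techniques for continuous measures.
- A reader might infer that factor-by-time terms merely copy the primary model. That model has no time terms. They are justified by the slope parameter, not by consistency with VIII.B.2.

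**Conclusion.** The omission is real and its direction is clear. As written, the random-regression model carries neither PTSD nor substance abuse. If either predicts HRSD slope, the reported standard error is too large and the test is conservative. The size is conditional on R²: roughly 0, 1.5, 3 or 7 power points at 0%, 5%, 10% or 20% of slope variance explained, given an adjusted model at 81% power, near-balanced allocation and a per-patient slope comparison.

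A reader might take this as a threat to the trial's conclusion, but it is not one. The primary logistic analysis already adjusts for all three factors, the treatment estimate in the slope model is not biased, and the error rate moves down, not up. The severity is minor: a free gain in a supportive analysis.

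**What to change.** In VIII.C.a, state that the short-term and longer-term random-regression models include PTSD diagnosis, history of substance abuse and site as covariates, the same three as in VIII.B.2. Because the tested parameter is a slope, add the interactions of PTSD and substance abuse with ln(t+1). If a statistical analysis plan already lists these terms, bring the protocol paragraph into line with it.

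The cost is wording only. History of substance abuse and PTSD diagnosis are items 7 and 8 of the randomisation form (Appendix E, Form 02), and site is recorded on every form. With 360 patients the added terms cost negligible degrees of freedom. In the simulation, adjusting when the factors had no effect left power unchanged (81.1% versus 81.2%).
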